4.2 Survival Follow-up/Event Monitoring

NOTE: Survival Follow-up/Event Monitoring on this study will cease as of 31Aug2025.

NOTE: Timelines are approximate and not meant to represent exact dates.

	Survival Follow-up		
	q. 6 months	Death	New Primary
Survival Follow-up ¹	X	X	At each occurrence

1. If a patient is still alive 5 years after registration, no further follow-up is required.

5.0 Grouping Factor

Enrollment Group: Safety run-in vs. phase II

6.0 Registration Procedures

6. Registration (Step 1)

To register a patient, access the Mayo Clinic Research Registration Application web page at [REDACTED]. The registration application is available 24 hours a day, 7 days a week. Back up and/or system support contact information is available on the website. If unable to access the website, contact Research Registration at [REDACTED] between the hours of 8 a.m. and 4:30 p.m. Central Time (Monday through Friday).

The instructions for the registration/randomization application are available on the Mayo Clinic Office of Clinical Trials web page [REDACTED]

[REDACTED] and detail the process for completing and confirming patient registration. Prior to initiation of protocol treatment, this process must be completed in its entirety and an MCCC subject ID number must be available as noted in the instructions. It is the responsibility of the individual registering the patient to confirm the process has been successfully completed prior to release of the study agent. Patient registration via the registration/randomization application can be confirmed in any of the following ways:

- Contact Mayo Clinic Research Registration Office [REDACTED] If the patient was fully registered, the Research Site Management staff can access the information from the centralized database and confirm the registration.
- Refer to “Instructions for Remote Registration” in section “Finding/Displaying Information about A Registered Subject.”

6.2 Verification of materials

Prior to accepting the registration, registration/randomization application will verify the following:

- IRB approval at the registering institution
- Patient eligibility
- Existence of a signed consent form
- Existence of a signed authorization for use and disclosure of protected health information

6.3 Documentation of IRB approval

Documentation of IRB approval must be on file in the Research Site Management Office before an investigator may register any patients.

In addition to submitting initial IRB approval documents, ongoing IRB approval documentation must be on file (no less than annually) with the Research Site Management Office [REDACTED] If the necessary documentation is not submitted in advance of attempting patient registration, the registration will not be accepted and the patient may not be enrolled in the protocol until the situation is resolved.

When the study has been permanently closed to patient enrollment, submission of annual IRB approvals to the Research Site Management Office is no longer necessary.

6.4 Patient Permissions

At the time of registration, the following will be recorded:

- Patient is or is not willing to complete questionnaires as part of this study
- Patient has/has not given permission for Mayo Clinic to have access to his/her recurrence/progression clinical sample(s) for research testing as part of this study.

6.5 Correlative Research

6.51 Mandatory

A mandatory correlative research component is part of this study, the patient will be automatically registered onto this component (see [Sections 3.1, 17.0](#)).

6.52 Banking

At the time of registration, the following will be recorded:

- Patient has/has not given permission to store and use his/her sample(s) for future research on cancer at Mayo Clinic.
- Patient has/has not given permission to store and use his/her sample(s) for future research to learn, prevent, or treat other health problems.
- Patient has/has not given permission for MCCC to give his/her sample(s) to researchers at other institutions.
- Patient has/has not given permission for Mayo Clinic to place coded genetic and medical information in secure databases for future research
- Patient has/has not given permission for Mayo Clinic to contact him/her for future research opportunities

6.6 Treatment on protocol

Treatment on this protocol must commence at Mayo Clinic under the supervision of a medical oncologist.

6.7 Treatment start

Treatment cannot begin prior to registration and must begin ≤ 7 days after registration.

6.8 Pretreatment

Pretreatment tests/procedures (see [Section 4.0](#)) must be completed within the guidelines specified on the test schedule.

6.9a Baseline symptoms

All required baseline symptoms (see [Section 10.6](#)) must be documented and graded.

6.9b Ophthalmology consult required

An ophthalmologist has seen the patient and confirms the patient is a suitable candidate for this study.

6.9c Study drug

Study drug is available on site.

6.9d Blood draw kits

Blood draw kit is available on site for sites outside of Rochester, MN.

6.9e Study Conduct

The clinical trial will be conducted in compliance with regulations (21 CFR 312, 50, and 56), guidelines for Good Clinical Practice (ICH Guidance E6), and in accordance with general ethical principles outlined in the Declaration of Helsinki; informed consent will be obtained from all participating patients; the protocol and any amendments will be subject to approval by the designated IRB prior to implementation, in accordance with 21 CFR 56.103(a); and subject records will be stored in a secure location and subject confidentiality will be maintained. The investigator will be thoroughly familiar with the appropriate use of the study drug as described in the protocol and Investigator's Brochure. Essential clinical documents will be maintained to demonstrate the validity of the study and the integrity of the data collected. Master files should be established at the beginning of the study, maintained for the duration of the study and retained according to the appropriate regulations.

7.0 Protocol Treatment

7.1 Treatment Schedule

Patients may receive treatment on this trial for up to 2 years until disease progression, unacceptable adverse events, or patient refusal.

7.11 Treatment medication table – Cycles 1-9

Agent	Dose Level	Route	Day	ReRx
futibatinib	20 mg*	oral	Once daily on Days 1-21	Q3w
pembrolizumab	200 mg	IV	1	Q3w

Cycle length = 21 days ± 3 days

*Investigator may start patients at lower dose (16mg) if clinically indicated (e.g., patient history of diarrhea) after discussion with PI

Once patients have completed Cycle 9, the cycle length can be increased to 6 weeks with imaging every other cycle (~12 weeks).

7.12 Treatment medication table – Cycles 10 and beyond

Agent	Dose Level	Route	Day	ReRx
futibatinib	20 mg	oral	Once daily on Days 1-42	Q6w
pembrolizumab	400 mg	IV	1	Q6w

Cycle length = 42 days ± 7 days

7.13 Futibatinib

Futibatinib is an oral agent taken once daily by mouth with water with or without food. Futibatinib should be taken at the same time every day.

On Day 1 of each cycle, the futibatinib dose should be held until at least 30 minutes after pembrolizumab infusion.

Futibatinib is supplied as 4 mg tablets and will be taken orally at a dose of 20 mg daily until the patient meets any of the administration discontinuation criteria.

In the event of a dosing delay up to 12 hours after the scheduled dosing time, the patient should still take that day's dose. If the dosing delay continues for >12 hours after the scheduled dosing time, or if the patient vomits after a dose, the patient should skip dosing for that day and not make up for it the following day.

7.14 Pembrolizumab

Pembrolizumab is given by IV infusion over 30 minutes (-5 or +10)

Pembrolizumab should be administered according to institutional guidelines for premedication and standard clinical care.

Pembrolizumab should be administered prior to futibatinib dose on Day 1.

7.2 Biopsies

If research biopsy material has already been obtained under IRB 17-003174 for this patient, then no additional research biopsy is needed specifically for this trial.

Tissue for FGF-19 testing can be from archived tissue or clinical biopsy as needed.

7.3 Return to consenting institution

For this protocol, the patient must return to the consenting institution for evaluation at least every 21 days ± 3 days during treatment for first 9 cycles. Beginning with Cycle 10 patients must return at least every 42 days ± 7 days.

7.4 Treatment by local medical doctor (LMD)

Treatment with futibatinib by a local medical doctor (LMD) is not allowed.

7.5 Safety Run-in for first six patients

Patients will receive futibatinib and pembrolizumab combination. The safety profile of both agents has been previously evaluated individually^{21,40}. To ensure the safety of this combination, we will perform a safety run-in with 6 patients. If there are 2 or more patients out of 6 who developed excessive toxicity during first cycle, the trial will be temporarily closed for enrollment to allow the study team to convene and discuss the best next steps.

7.51 For this protocol, excessive toxicity will be defined as follows:

Adverse event at least possibly related to the study medication	Definition using CTCAE v5.0
Any*	Grade 3 resulting in treatment interruption of both drugs for more than 21 days
Blood and lymphatic system disorders: Anemia	Grade 3 lasting >3 days
Any*	Grade 4
Investigations: Absolute neutrophil count decreased	Grade 4 lasting >7 days
Any	Grade 5
Gastrointestinal disorders 
 • Diarrhea • Nausea • Vomiting 	Grade 3 lasting >3 days with optimal supportive care

*Exceptions for: anemia, absolute neutrophil count; transient laboratory values without clinical manifestation; bowel obstruction resulting in hospitalization as a consequence of disease; which will not count as excessive toxicity

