10.32 EXPECTED Serious Adverse Events: Protocol Specific Exceptions to Expedited Reporting

For this protocol only, the following Adverse Events/Grades are expected to occur within this population and do not require Expedited Reporting. These events must still be reported via Routine Reporting (see Section 10.6).*

*Report any clinically important increase in the rate of a serious suspected adverse reaction (at your study site) over that which is listed in the protocol or investigator brochure as an expedited event.

*Report an expected event that is greater in severity or specificity than expected as an expedited event.

*Specific protocol exceptions to expedited reporting should be reported expeditiously by investigators **ONLY** if they exceed the expected grade of the event.

CTCAE System Organ Class (SOC)	Adverse event/ Symptoms	CTCAE Grade at which the event will not be reported in an expedited manner ¹
Blood and lymphatic system disorders	Anemia	≤Grade 4
Gastrointestinal disorders	Diarrhea	≤Grade 3
	Nausea	≤Grade 3
	Vomiting	≤Grade 3
General disorders and administrations site conditions	Fatigue	≤Grade 3
	Malaise	≤Grade 3
Investigations	Lymphocyte count decreased	≤Grade 4
	Neutrophil count decreased	≤Grade 4
	Platelet count decreased	≤Grade 4
	White blood cell count decreased	≤Grade 4

¹ These exceptions only apply if the adverse event does not result in hospitalization. If the adverse event results in hospitalization, then the standard expedited adverse events reporting requirements must be followed.

The following hospitalizations are not considered to be SAEs because there is no “adverse event” (*i.e.*, there is no untoward medical occurrence) associated with the hospitalization:

- Hospitalization prior to signing main study consent
- Hospitalizations for respite care
- Planned hospitalizations required by the protocol
- Hospitalization planned before informed consent (where the condition requiring the hospitalization has not changed post study drug administration)
- Hospitalization for elective procedures unrelated to the current disease and/or treatment on this trial
- Hospitalization for administration of study drug or insertion of access for administration of study drug

- Hospitalization for routine maintenance of a device (e.g., battery replacement) that was in place before study entry
- Hospitalization, or other serious outcomes for signs and symptoms of progression of the cancer.

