16.72 Adverse Event Stopping Rules

The stopping rules specified below are based on the knowledge available at study development. We note that the Adverse Event Stopping Rule may be adjusted in the event of either (1) the study re-opening to accrual or (2) at any time during the conduct of the trial and in consideration of newly acquired information regarding the adverse event profile of the treatment(s) under investigation. The study team may choose to suspend accrual because of unexpected adverse event profiles that have not crossed the specified rule below.

Accrual will be temporarily suspended to this study if at any time, we observe events considered to be at least possibly related to study treatment (i.e., an adverse event with attribute specified as “possible”, “probable”, or “definite”) that satisfy the following:

- If at any time, 4 of the initial 10 treated patients or 40% or more of all patients (i.e., when accrual is greater than 10 patients) have experienced a Grade 4+ adverse event at least possibly related to study treatment. per NCI Common Terminology Criteria for Adverse Events v.5.0, excluding the following:
 - Grade 4 white blood cell decreased lasting ≤ 3 days
 - Grade 4 platelet count decreased lasting ≤ 3 days
 - Grade 4 electrolyte alteration* lasting ≤ 3 days

*Electrolyte alterations include the following events in SOC
“Metabolism and nutrition disorders”

- Hyperglycemia or Hypoglycemia
- Hyperkalemia or Hypokalemia

We note that we will review Grade 4 and 5 adverse events deemed “unrelated” or “unlikely to be related”, to monitor the emergence of a previously unrecognized treatment-related adverse event.

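### The run-in toxicity definition counts Grade 3 anemia lasting more than 3 days, but no row counts Grade 4 anemia

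*Combined protocol and SAP*

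**What the plan says.** Section 7.5 (Safety Run-in) temporarily closes enrollment if there are "2 or more patients out of 6 who developed excessive toxicity during first cycle". Section 7.51 defines excessive toxicity by a table of events at least possibly related to study medication. Its rows are:

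- Any event (starred): Grade 3 with both drugs interrupted for more than 21 days.
- Anemia: "Grade 3 lasting >3 days".
- Any event (starred): Grade 4.
- Neutrophil count decreased: "Grade 4 lasting >7 days".
- Any event (no star): Grade 5.
- Diarrhea, nausea or vomiting: Grade 3 for more than 3 days despite optimal supportive care.

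One footnote serves both starred rows. It begins "Exceptions for: anemia, absolute neutrophil count; transient laboratory values without clinical manifestation" and ends by stating that the listed items do not count as excessive toxicity.

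**The concern.** Because the footnote takes anemia and neutrophil count out of both starred rows, each can count below Grade 5 only through its own row. The neutrophil row supplies a Grade 4 criterion. The anemia row stops at Grade 3. A toxicity definition should not drop an event as it becomes more severe, and this one does.

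The event is foreseeable. Section 15.17 lists anemia among the most common adverse events (15% or more) in all three futibatinib daily-dosing studies. Section 3.16 admits patients with hemoglobin as low as 8.0 g/dL, and Section 8.21 has a separate action for Grade 4 anemia.

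At stake is the Cycle 1 enrollment pause, the specific check placed on the combination before accrual proceeds. The PFS6 endpoint, type I error, power and sample size do not depend on it.

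**Working it through.** **Step 1. Classify related Cycle 1 anemia by the Section 7.51 table as written.**

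| Anemia | Starred Grade 3 row | Anemia row | Starred Grade 4 row | Grade 5 row | Counts? |
|---|---|---|---|---|---|
| Grade 3, 4 days | excepted | met | – | – | Yes |
| Grade 4, 10 days | – | not met (names Grade 3 only) | excepted | – | No |
| Grade 5 | – | – | – | met (no star) | Yes |

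A Grade 4 episode enters the count only if it also spends more than 3 days at Grade 3, or becomes fatal. Sections 9.1 and 9.2 allow blood products, so an episode can be corrected without that interval. An episode that stays at Grade 4 also misses it.

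**Step 2. Look for another rule that restores the count.**

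- Section 16.72 counts related Grade 4 or higher events and does not exclude anemia, but its threshold is "4 of the initial 10 treated patients or 40% or more of all patients". That is 40%, against 2/6 = 33% for the run-in.
- Section 10.32 exempts anemia up to Grade 4 from expedited reporting, subject to "These exceptions only apply if the adverse event does not result in hospitalization" and to the instruction "Report any clinically important increase in the rate of a serious suspected adverse reaction". This governs reporting, not the count.
- Section 8.21 (futibatinib omitted at Grade 4 anemia) and Section 16.71 (monthly review) do not change the definition.

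None of these puts Grade 4 anemia into the 2-of-6 count.

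**Step 3. Size the effect.** The plan states no operating characteristics for the run-in, so there is no figure to reproduce. The inputs are n = 6 and a trigger of 2 (Section 7.5), plus two assumed rates:

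- p: per-patient rate of toxicity that counts as written.
- q: per-patient rate of related Cycle 1 Grade 4 anemia with no more than 3 days at Grade 3 and no other counted event.

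For a counted rate r, P(2 or more of 6) = 1 − (1 − r)^6 − 6r(1 − r)^5. The rule as written uses r = p; counting every Grade 4 anemia uses r = p + q.

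Example: at r = 0.10, 1 − 0.5314 − 0.3543 = 0.1143. At r = 0.11, 1 − 0.4970 − 0.3685 = 0.1345. The gap is 2.0 percentage points.

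| q (assumed) | p = 10%: as written → corrected | Gap (points) | p = 20%: as written → corrected | Gap (points) |
|---|---|---|---|---|
| 0.5% | 11.4% → 12.4% | 1.0 | 34.5% → 35.7% | 1.2 |
| 1% | 11.4% → 13.4% | 2.0 | 34.5% → 36.9% | 2.5 |
| 2% | 11.4% → 15.6% | 4.1 | 34.5% → 39.4% | 4.9 |
| 5% | 11.4% → 22.4% | 10.9 | 34.5% → 46.6% | 12.1 |
| 10% | 11.4% → 34.5% | 23.0 | 34.5% → 58.0% | 23.5 |

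Gaps are taken from unrounded probabilities. Because q describes a narrow subset, the upper rows of the table are more plausible than the lower ones.

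Under a lighter repair that counts only Grade 3 or higher lasting more than 3 days, q is replaced by the part of it meeting that duration. If that were half of q = 2%, for example, the q = 1% row would apply.

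**The case against.** The strongest reply is that the table can be read differently. Each specific row sits directly below the starred row it seems to modify: anemia below the Grade 3 row, neutrophil count below the Grade 4 row. On that pairing, anemia is excepted only at Grade 3 and Grade 4 anemia still counts. Alternatively, the Grade 3 criterion could be taken as a floor that a longer Grade 4 episode also meets.

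Both readings are reasonable guesses at intent, but the text does not support them. The star on the Grade 4 row leads to a footnote that names anemia without limiting it by grade. The floor reading conflicts with the table's separate rows for Grades 3, 4 and 5, and with the rest of the protocol, which says so explicitly when it means a grade and above (Sections 9.4 and 16.72).

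The objections on consequence are stronger, and they stand:

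- The trigger is only a temporary pause for discussion.
- Planned accrual is 2 patients a month (Section 16.3) with monthly review, so the team would see each event. Section 16.72 adds that it "may choose to suspend accrual because of unexpected adverse event profiles that have not crossed the specified rule below".
- Many Grade 4 episodes will pass through Grade 3 on recovery, and some of those will count.
- Both p and q are assumed.
- Section 1.4 reports 11 FGF19-positive patients enrolled by Amendment 4, so the run-in is apparently over.

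Counting Grade 4 anemia with no duration limit also goes further than restoring grade order requires.

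**Conclusion.** The definition is wrong as written. Related Grade 4 anemia meets no row of the run-in rule, while Grade 3 anemia of more than 3 days and Grade 5 anemia both do. This rests on the text alone and needs no assumption about rates.

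The practical effect is minor. At the more plausible residual rates of 0.5% to 1%, the probability of a pause is understated by 1.0 to 2.5 points for other counted toxicity of 10% or 20%. Larger gaps need residual rates that nothing in the documents supports. These figures assume independent patients with a common rate and a correction that counts every Grade 4 anemia. Nothing in the documents shows that an event was missed.

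**What to change.** Rewrite the anemia row in Section 7.51 as Grade 3 lasting more than 3 days, or Grade 4. That brings anemia into line with the general Grade 4 row. If a duration limit is wanted, Grade 3 or higher lasting more than 3 days is the least that restores grade order.

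Because the run-in is apparently complete, the edit mainly corrects the rule on record. The useful step is to re-check the six run-in patients' Cycle 1 records against the corrected row and report whether the 2-of-6 conclusion changes.

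The cost is one table row and a review of six existing records, with no new data collection.

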8.0 Dosage Modification Based on Adverse Events

Strictly follow the modifications in this table for the first **two** cycles, until individual treatment tolerance can be ascertained. Thereafter, these modifications should be regarded as guidelines to manage mild-to-moderate, but not debilitating, side effects. If multiple adverse events are seen, administer dose based on greatest reduction required for any single adverse event observed.

Reductions or increases apply to treatment given in the preceding cycle and are based on adverse events observed since the prior dose.

Special Considerations

- The treating investigator may reduce/withhold/discontinue a patient's dose for an AE of any grade/duration where s/he believes it to be in the best interests of the patient.
- In patients who have met the criteria for permanent discontinuation, resumption of futibatinib may be considered if the patient is deriving clinical benefit and has fully recovered from the related event after consulting with PI.
- Any consideration to modification of the above dose modification guidelines should be discussed with the Principal Investigator for approval or disapproval in advance.

→ ***ALERT: ADR reporting may be required for some adverse events (See Section 10.0)*** ←

8.1 Dose Levels (Based on Adverse Events in Tables 8.2 and 8.3)

Dose Level	Futibatinib (TAS-120)	Pembrolizumab Cycles 1-9	Pembrolizumab Cycles 10+
1 *	20 mg	200 mg q3w	400mg q6w
-1	16 mg	--	--
-2	12 mg	--	--

*Dose level 1 refers to the starting dose.

Patients may be started at dose -1 if clinically indicated after discussion with PI

NOTE: If either of futibatinib or pembrolizumab is discontinued, the patient can continue on the other drug, unless specified otherwise in the dose modification tables. If both are discontinued, the patient will go to survival follow-up (Section 4.2).

→ → ***Use the NCI Common Terminology Criteria for Adverse Events (CTCAE) current version 5.0* unless otherwise specified*** ← ←

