4.0 Test Schedule

4.1 Test schedule for Hepatocellular Carcinoma (HCC)

Tests and procedures ¹	Screening ≤21 days prior to registration	Active Monitoring Phase							Obs Clinical follow-up ⁴
		After Reg prior to C1D1 Tx	Cycle 1 Days 8, 15	End of every cycle	End of every 3 cycles (Cycles 1-9) ²	End of every 2 cycles (Cycles 10+) ³	End of treatment	Safety follow-up: 30 days post treatment	
Window			±3 days	±3 days	±7 days	±7 days	±7 days	±7 days	±7 days
History and exam, Wt, PS	X		X	X			X	X	X
Height	X								
Adverse event assessment ⁵	X	X	X	X	X	X	X	X	
Pregnancy test ⁶	X								
Hematology group: CBC /w diff	X ⁷		X	X			X	X	
Chemistry group ⁸	X ⁹		X	X			X	X	
TSH	X			X			X	X	
Ophthalmologic testing ¹⁰	X				X ¹¹	X ¹²			
Nutrition consult ¹³				X					
FGF19 testing ^R			X ¹⁴						
AFP, AFP-L3 % ¹⁵	X				X	X			

Cycle = 21 days ±3 days for Cycles 1-9; Cycle = 42 days ±7 days for Cycles 10+; R= Research funded (See [Section 19.0](#))

¹ All tests and procedures should be performed as needed for clinical care at treating physician's discretion.

² End of Cycles 3, 6, 9 (NOTE: Imaging schedule may be adjusted by treating oncologist as necessary for clinical care.)

³ End of Cycles 11, 13, 15, etc. (NOTE: Imaging schedule may be adjusted by treating oncologist as necessary for clinical care.)

⁴ Observation: every 9 weeks until disease progression, new anti-cancer therapy, death, withdrawal from clinical follow-up, or a maximum of 18 month post registration.

⁵ AEs must be assessed at every cycle; Baseline AE collection for eligibility should be done after patient signs main study consent

⁶ For persons of childbearing potential only: Must be done ≤7 days prior to registration and repeated prior to C1D1 if >7 days between registration and treatment.

⁷ Eligibility requires ≤15 days prior to Registration

⁸ Chemistry: comprehensive metabolic panel (CMP) (80053) plus phosphorus (84100)

⁹ Eligibility requires ≤15 days prior to Registration

¹⁰ Must include external ocular exam; routine slit lamp biomicroscopy of anterior ocular structures include the anterior and posterior chambers; dilation of the pupil with direct/indirect fundoscopy per institutional guidelines; must be done ≤6 months prior to treatment and 2 months after first dose of futibatinib and every 2 months until 6 months after first dose, and every 3 months thereafter and urgently at any time for visual symptoms.

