11.45 Symptomatic Deterioration

Patients with global deterioration of health status requiring discontinuation of treatment without objective evidence of disease progression at that time, and not either related to study treatment or other medical conditions, should be reported as PD due to "symptomatic deterioration." Every effort should be made to document the objective progression even after discontinuation of treatment due to symptomatic deterioration. A patient is classified as having PD due to "symptomatic deterioration" if any of the following occur that are not either related to study treatment or other medical conditions:

- Weight loss >10% of body weight.
- Worsening of tumor-related symptoms.
- Decline in performance status of >1 level on ECOG scale.

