13.0 Treatment/Follow-up Decision at Evaluation of Patient

- 13.1 Continuation of treatment

Patients who are CR, PR, or SD will continue treatment per protocol.

- 13.2 Progressive disease (PD)

Patients who develop PD while receiving therapy will go to the survival follow-up phase.

- 13.3 Off protocol treatment

Patients who go off protocol treatment for reasons other than PD will go to the clinical follow-up/observation phase per Section 4.0. Participants will be required to return to the consenting site for follow-up until disease progression, new anti-cancer therapy, death, withdrawal of consent for clinical followup, or a maximum of 18 months from Registration.

- 13.4 Duration of therapy for CR

Patients who achieve a CR will receive a maximum total of 35 cycles (i.e., 2 years). After 35 cycles, they will go to survival follow-up/event monitoring. Subsequent treatment is at the discretion of their attending physician.

- 13.5 Duration of therapy for PR or SD

Patients who are in PR or SD will continue on therapy for a total of 35cycles (i.e., 2 years). After 35 cycles, they will go to survival follow-up/event monitoring. Subsequent treatment is at the discretion of their attending physician.

- 13.6 Ineligible

A patient is deemed *ineligible* if after registration, it is determined that at the time of registration, the patient did not satisfy each and every eligibility criteria for study entry. If the patient received treatment, the patient may continue treatment at the discretion of the physician as long as there are not safety concerns. The patient will continue in the Active Monitoring/Treatment phase of the study, per [Section 4.0](#) of the protocol.

- If the patient never received treatment, on-study material must be submitted. Survival follow-up/event monitoring will be required per [Section 4.0](#) of the protocol.

- 13.7 Major violation

A patient is deemed a *major violation*, if protocol requirements regarding treatment in Cycle 1 of the initial therapy are severely violated that evaluability for primary endpoint is questionable. If the patient received treatment, the patient may continue treatment at the discretion of the physician as long as there are not safety concerns. The patient will continue in the Active Monitoring/Treatment phase of the study, per [Section 4.0](#) of the protocol.

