13.8 Cancel

A patient is deemed a *cancel* if he/she is removed from the study for any reason before any study treatment is given. On-study material and the End of Active Treatment/Cancel Notification Form must be submitted. No further data submission is necessary.

13.9a Subsequent Anti-Cancer Therapy Status

The investigator or qualified designee will review all new anti-neoplastic therapy initiated after the last dose of trial treatment. If a participant initiates a new anti-cancer therapy within 30 days after the last dose of trial treatment, the 30-day Safety Follow-up visit must occur before the first dose of the new therapy. Once new anti-cancer therapy has been initiated the participant will move into survival follow-up/event monitoring per [Section 4.0](#).

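### Sections 8.1 and 13.3 send patients who stop both drugs without progression to different follow-up, and only one route schedules the progression scans that PFS6 needs

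*Combined protocol and SAP*

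**What the plan says.** The note under the dose-level table in Section 8.1 first allows single-drug continuation: "If either of futibatinib or pembrolizumab is discontinued, the patient can continue on the other drug". It then says: "If both are discontinued, the patient will go to survival follow-up (Section 4.2". It does not distinguish reasons for stopping, but the table is headed as based on adverse events. Section 4.2 lists contact every 6 months, death and new primary. It has no tumor measurement and no progression item.

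Section 13.3 says: "Patients who go off protocol treatment for reasons other than PD will go to the clinical follow-up/observation phase per Section 4.0". Footnote 4 of the 4.1 schedule describes that phase: "Observation: every 9 weeks until disease progression, new anti-cancer therapy, death", withdrawal, or 18 months after registration. The tumor measurement row of 4.1 is marked both at end of treatment and in the observation column. Section 13.2 deals with progression: "Patients who develop PD while receiving therapy will go to the survival follow-up phase".

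The primary endpoint (16.1) is PFS at 27 weeks from registration. Under 16.3 a patient is evaluable if eligible, consented, FGF19-positive, given any protocol treatment and free of major violation. Stopping early does not remove a patient.

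**The concern.** A patient who stops both drugs for toxicity, without progression, falls under both 8.1 and 13.3, which give different destinations. One continues 9-weekly imaging; the other does not. The choice therefore decides whether later progression is looked for in a patient who counts in the primary analysis. With 22 evaluable patients each one is 1/22 = 4.5% of the sample, and the go/no-go decision is a fixed threshold. Primary-endpoint data should not depend on which section a site happens to read.

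**Working it through.** **The two routes side by side, for a patient who stops both drugs without progression before week 27**

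| Item | 8.1 with 4.2 | 13.3 with 4.1 |
|---|---|---|
| End-of-treatment scan | Yes | Yes |
| Later tumor measurement | None scheduled | Every 9 weeks |
| Death | Recorded | Recorded |
| After new anti-cancer therapy | No scans | No scans |

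The routes differ only in scans after the end-of-treatment scan, in patients who have not started new therapy. For patients who stop because of progression, 8.1 and 13.2 agree.

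**The plan's own figures.** Section 16.5 gives a probability of declaring success of 0.7923 at a true 47% and 0.0651 at 25%. With complete follow-up, the 80% logit-Greenwood lower bound is 0.245 at 8/22 and 0.284 at 9/22, so success needs 9 of 22. The exact binomial gives P(X≥9) = 0.783 at 47% and 0.075 at 25%. Simulating the stated Weibull models with the interim applied as a stop gives 0.785 and 0.056. These are close enough to use the rule below. The interim is ignored from here on because it is non-binding.

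**Illustration at a true PFS6 of 25%.** From the plan: the null Weibull shape 0.6667, rescaled so that S(27) = 0.25; N = 22; the success rule. Assumed, because the documents are silent:
- a share f of all patients stops both drugs at week 9, progression-free;
- r is their chance of remaining progression-free to week 27 relative to continuing patients;
- a share d of their later failures is recorded as deaths, and all other stoppers are censored at week 9.

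Steps:
1. S(9) = 0.25^((9/27)^0.6667) = 0.5135.
2. Stoppers among those at risk at week 9: w = f/0.5135.
3. Continuing patients' conditional survival to week 27: c = (0.25/0.5135)/(wr + 1 − w).
4. Large-sample Kaplan-Meier under 8.1: 0.5135 × (1−w)c / [(1−w) + w·d·(1−rc)].

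Worked case f = 0.10, r = 0.5, d = 0.4: w = 0.1947 and c = 0.5393, so the numerator is 0.8053 × 0.5393 = 0.4343. The denominator is 0.8053 + 0.1947 × 0.4 × 0.7303 = 0.8622. The estimate is 0.5135 × 0.4343/0.8622 = 25.9%.

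Results from 200,000 simulated trials, f = 5/10/15/20% (about 1/2/3/4 patients):

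| r, d | Mean Kaplan-Meier, % | P(declare success) |
|---|---|---|
| Complete follow-up | 25.0 | 0.075 |
| 0.5, 0.4 | 25.5/25.9/26.2/26.3 | 0.10/0.11/0.13/0.13 |
| 0.75, 0.4 | 24.9/24.8/24.5/24.1 | 0.09 throughout |
| 1, 0.4 | 24.4/23.9/23.0/22.1 | 0.08/0.08/0.07/0.06 |
| 0.5, 0.6 | 25.0/25.1/24.9/24.5 | 0.09-0.10 |
| 1, 0 (censoring uninformative) | 25.0 | 0.09/0.10/0.11/0.11 |
| 0.5, 0 (extreme: no deaths recorded) | 26.3/27.7/29.3/31.0 | 0.12/0.16/0.21/0.26 |

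Uncollected progression pushes the estimate up. Counting deaths while dropping progression-free follow-up in the same patients pushes it down. The uninformative row has no bias, yet its false-positive rate still rises from 0.075 to between 0.09 and 0.11. Part of any such rise therefore comes from censoring loosening a discrete 9-of-22 rule, not from bias.

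**What the 13.3 route recovers.** If half the stoppers start new therapy at week 9 and lose scans anyway (d = 0.4), r = 0.5 gives 25.2-25.6% and 0.09-0.11, and r = 1 gives 24.7-23.8% and about 0.08.

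**The case against.** The strongest reply is that the rest of the protocol already shows the intent. Section 13 is the section on follow-up decisions. Read literally for all stoppers, 8.1 would leave almost nobody for the observation column of 4.1, and 18.5 asks for documentation of progression after study therapy. The Data Submission Schedule and Forms Packet are not part of these documents, so loss of progression data is possible, not shown. This stands as a reason to treat 8.1 as the probable outlier. It does not remove the conflict: 8.1 is the note a site reads when stopping drugs for toxicity, and 18.5 sets no scan schedule.

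The affected group may also be small. One drug may continue, Section 8.0 allows futibatinib to be resumed after discontinuation criteria are met, and 11.45 classes as progression "Patients with global deterioration of health status requiring discontinuation of treatment without objective evidence of disease progression at that time", if it is not due to treatment or another condition. That stands too.

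A reader might infer three stronger things that the documents do not support.
- *Survival follow-up is reserved for progression, so 8.1 must be wrong.* Sections 13.4 and 13.5 send patients there after 35 cycles, 13.6 sends untreated ineligible patients, and 13.9a says: "Once new anti-cancer therapy has been initiated the participant will move into survival follow-up/event monitoring per" Section 4.0. The conflict rests on 13.3 with 4.1.
- *Everyone who stops both drugs goes unscanned.* The 8.1 note sits under adverse-event modification, and the end-of-treatment scan is kept on either route.
- *PFS6 is inflated.* The direction changes with the assumptions, and the highest false-positive figures need no stopper's death to be recorded, although 4.2 records deaths.

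**Conclusion.** The plan is wrong as written: 8.1 and 13.3 with 4.1 give different follow-up to the same patients, and no section says which prevails. Following 8.1 leaves progression after the end-of-treatment scan unscheduled for patients who stop both drugs without progression before week 27 and who remain evaluable for PFS6.

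That conclusion rests on the text alone. The size and direction of any effect are not established, because the documents give no rate of stopping both drugs and Section 16 states no PFS censoring rule. Censoring at the last scan is an assumption made here. With 5-20% stopping at week 9, r from 0.5 to 1 and 40% of later failures recorded as deaths, the mean estimate for a true 25% runs from about 22% to 26%. The documents do not show a large effect. The reason to act is that the ambiguity touches primary-endpoint data and is cheap to remove.

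**What to change.** Reconcile the 8.1 note with 13.3, 4.1 and 4.2, so that the follow-up cross-reference for patients without progression is the same in each place and the progression scans already scheduled in 4.1 are collected through week 27. For any patient already moved to survival follow-up without progression before week 27, retrieve existing clinical scans and count deaths as PFS events.

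The cost is a one-sentence amendment with IRB approval (6.9e) and no new visits. It has limits. It does not recover scans after new anti-cancer therapy, and it does not supply the missing censoring rule. A prospective correction helps only patients not yet past week 27, and survival follow-up ends on 31 August 2025; for the others, retrieving existing scans is what remains. An added analysis counting every unscanned stopper as a failure would be a matter of preference; this point does not require it.
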